### 4.2.3 Rationale for Endpoints

#### 4.2.3.1 Efficacy Endpoints

The primary efficacy objective of this study is to determine if the ORR of patients with *PD-L1* gene-altered DLBCL to pembrolizumab monotherapy is higher than that of a historical cohort of unselected DLBCL patients. Response in this study will be assessed according to LYRIC criteria (modified from Lugano response criteria) (1). If the primary hypothesis is proven correct, then a confirmatory, retrospective radiographic review of response in each patient will be performed in collaboration with an outside vendor.

The LYRIC criteria were chosen for designating response in this clinical trial because immunotherapeutic agents such as pembrolizumab mediate anti-tumor effects by potentiating endogenous cancer-specific immune responses. Responses to immunotherapeutic agents occasionally occur in a delayed fashion - often beyond the typical time frame of that expected following treatment with classical cytotoxic agents. Furthermore, in the context of checkpoint blockade immunotherapy, clinical responses can occur even after an initial increase in tumor burden is observed, or even after the appearance of new lesions on imaging studies, due to inflammation in sites of tumor activity and in areas uninvolved by malignancy. The LYRIC criteria represent the most up-to-date consensus guidelines for response assessment of lymphomas treated with immunomodulatory agents such as pembrolizumab, and were created by international experts. Importantly, the LYRIC criteria incorporate an indeterminate response category that allows for continued treatment in clinically stable/improving patients who would otherwise be deemed to have progressive disease using conventional response criteria. This is a significant addition to standard response criteria for immune-based therapies as evidenced by a recent study of PD-1 blockade in cHL, in which 61% of patients treated beyond conventional disease progression demonstrated stable or further reduced target tumor burdens (25). Therefore, patients with an indeterminate response in the current study will be able to continue treatment with pembrolizumab if deemed appropriate by the treating physician. These patients must undergo repeat imaging within 12 weeks to either confirm that an objective tumor response has occurred, or to unequivocally document disease progression. Overall, the LYRIC criteria are anticipated to allow for a more accurate assessment of the true clinical benefit from immunotherapies such as pembrolizumab, and are now recommended to be utilized as the standard response criteria for lymphoma clinical trials incorporating immunotherapies (1).

#### 4.2.3.2 Biomarker Research

**4.2.3.2.1 Utility of *PD-L1* gene alterations to predict ORR and PFS to pembrolizumab in DLBCL.** The ORR of unselected relapsed/refractory DLBCL patients to PD-1 blockade is low (33). Predictive biomarkers of response are therefore needed in order for pembrolizumab to have a clinically meaningful impact in the treatment of DLBCL. Based on our preliminary data, we hypothesize that the identification and selection of patients with *PD-L1* gene-altered DLBCLs for pembrolizumab therapy will enrich for treatment responseiveness compared to what has been observed in unselected DLBCL patients. This hypothesis is based upon our findings indicating that *PD-L1* gene-altered lymphomas are associated with robust anti-tumor immune responses. In this clinical trial, the presence of *PD-L1* gene alterations will be determined using a validated fluorescent *in-situ* hybridization (FISH) assay (Appendix 1). In order to determine the utility of

*PD-L1* gene alterations to predict for response to pembrolizumab, the ORR to pembrolizumab in this study will be compared to that of a historical cohort of 40 unselected DLBCL patients treated with pembrolizumab in the KEYNOTE-013 study, where the ORR was 13%. Additionally, we will determine whether a correlation exists between the degree of *PD-L1* alteration (amplification/translocation > relative copy gain > chromosome 9 polysomy) and best overall response (BOR) and PFS, as was the case in cHL patients treated with PD-1 blockade therapy (45). Finally, as our preliminary data reveal that only ~65% of *PD-L1* altered DLBCLs are PD-L1 positive by immunohistochemistry, we will compare the ORR of DLBCLs with positive PD-L1 protein expression on malignant cells as assessed by IHC versus those with absent PD-L1 staining in order to ascertain whether PD-L1 protein expression should be considered as a companion diagnostic with FISH for *PD-L1* gene alterations to improve the positive predictive value of this biomarker moving forward.

**4.2.3.2.2 Effect of tumor cell intrinsic and environmental factors on responsiveness to pembrolizumab in DLBCL.** Previous studies have demonstrated an impact of both tumor cell intrinsic and environmental factors, as well as other host variables, such as the intestinal microbiome, on responsiveness to anti-PD-1 therapies in a variety of solid tumor malignancies (46-48). To determine whether these features also influence responsiveness to PD-1 blockade in DLBCL, whole exome sequencing (WES) and RNA sequencing (seq) will be performed on pre-treatment biopsies, and baseline stool samples will be collected prior to commencing study therapy with pembrolizumab. WES of tumor samples will be performed through Theragen Etex, while RNA-seq, bioinformatics analysis, and microbiome analysis will all be conducted in core facilities at The University of Chicago.

**4.2.3.2.3 Feasibility of utilizing circulating tumor DNA (ctDNA) to predict early response to pembrolizumab in DLBCL, and to identify genetic mechanisms that underlie acquired resistance to therapy.** The quantification of ctDNA can be a sensitive marker of response to a wide array of therapies in a number of tumor types while also providing valuable prognostic information (49, 50). Furthermore, ctDNA offers a non-invasive method of serially monitoring the clonal evolution of tumors responding to a particular therapy, and may also identify mutations or other genomic alterations associated with emerging resistance. Currently, there are no data on the use of ctDNA to monitor response, clonal evolution or resistance to anti-PD-1 therapy, and the mechanisms of acquired resistance to pembrolizumab in DLBCL are unknown. To investigate the hypothesis that serial ctDNA monitoring will provide early response information to pembrolizumab, and will identify mutations in genes critical for maintaining immune surveillance in patients developing acquired resistance to therapy, plasma will be collected for ctDNA analysis at baseline and after every 4 cycles of therapy (in parallel with disease response assessment via conventional imaging). All ctDNA analyses will be performed using a customized lymphoma panel created at the Cancer Precision Medicine Center in the Cancer Institute of Japanese Foundation for Cancer Research.

#### **4.2.3.3 Future Biomedical Research**

It is possible that Future Biomedical Research will be conducted on blood and lymph node specimens collected during this clinical trial. This research may include genetic analyses (DNA), gene expression profiling (RNA), proteomics, metabolomics (serum, plasma), and/or the measurement of other analytes.

Such research is for biomarker testing to address emergent questions not described elsewhere in the protocol (as part of the main trial). The objective of collecting specimens for Future Biomedical Research will be to explore and identify biomarkers that inform the scientific understanding of diseases and/or their therapeutic treatments. The details of Future Biomedical Research are presented in Appendix 6 – Collection and Management of Specimens for Future Biomedical Research.

#### **4.3 Benefit/Risk**

It cannot be guaranteed that subjects in clinical trials will directly benefit from treatment during participation, as clinical trials are designed to provide information about the safety and effectiveness of an investigational medicine.

Efficacy and safety information in regards to pembrolizumab are provided in the current version of the IB.

### **5.0 METHODOLOGY**

#### **5.1 Study Population**

Relapsed/refractory DLBCL patients with evidence of *PD-L1* gene alterations (copy number alterations or translocations) as determined by FISH.

##### **5.1.1 Participant Inclusion Criteria**

Participants are eligible to be included in the study if all of the following criteria apply:

1. Male/female participants who are at least 18 years of age on the day of signing informed consent with a histologically confirmed diagnosis of DLBCL will be enrolled in this study.

*Note: Patients with high-grade B cell lymphomas not otherwise specified and those with MYC and BCL2 translocations (double hit lymphoma) are eligible, as are patients with transformed indolent lymphoma, so long as PD-L1 gene alterations are present.*

2. A male participant must agree to use a contraception as detailed in Appendix 4 of this protocol during the treatment period, and for at least 120 days after the last dose of study treatment and refrain from donating sperm during this period.
3. A female participant is eligible to participate if she is not pregnant (see Appendix 4), not breastfeeding, and at least one of the following conditions applies:
  - a.) Not a woman of childbearing potential (WOCBP) as defined in Appendix 4
  - b.) A WOCBP who agrees to follow the contraceptive guidance in Appendix 4 during the treatment period and for at least 120 days after the last dose of study treatment.
  - c.) patient must have negative pregnancy test within 72 hours of beginning treatment if WOCBP
4. The participant (or legally acceptable representative if applicable) provides written informed consent for the trial.

5. Have measurable disease, defined as at least one lesion that can be accurately measured in at least two dimensions by CT scan. Minimum measurement must be >15 mm in the longest diameter by >10 mm in the short axis. Lesions situated in a previously irradiated area are considered measurable if radiographic progression has been demonstrated in such lesions.

6. Participants must have available archived biopsy material (ideally to be performed shortly before enrollment at the time of most recent relapse) for *PD-L1* FISH and correlative studies. Formalin-fixed, paraffin embedded (FFPE) tissue blocks are preferred to slides.

*Note: If submitting unstained cut slides, newly cut slides should be submitted within 14 days from the date slides are cut if possible.*

7. There is evidence of a *PD-L1* gene alteration within lymphoma cells as assessed by FISH. See Appendix 1 for detailed description of what constitutes the presence of a *PD-L1* gene alteration.

8. Participants must have received either:

- a.  $\geq 2$  lines of prior systemic therapy
- b.  $\geq 1$  line of prior systemic therapy with documented comorbidities that preclude eligibility for standard salvage chemotherapy and autologous stem cell transplant , or
- c. 1 line of prior therapy with documented disease relapse within 12 months of initial diagnosis.

*Note: patients having undergone prior CAR T cell therapy are eligible, as are patients having received a prior allogeneic transplantation, provided they do not meet any of the exclusionary GVHD criteria, and are at least 5 years removed from the date of their transplant.*

9. Have an Eastern Cooperative Oncology Group (ECOG) performance status of 0 to 1. Evaluation of ECOG performance status is to be performed within 14 days prior to the date of treatment allocation.

10. Have adequate organ function as defined in Table 1 within 10 days prior to the date of treatment allocation.

Table 1. Adequate Organ Function Laboratory Values

System	Laboratory Value
Hematological	
Absolute neutrophil count (ANC)	$\geq 1,000/\mu\text{L}$

Platelets	$\geq 50,000/\mu\text{L}$
Hemoglobin	$\geq 8.0 \text{ g/dL}^a$
Renal	
Creatinine OR Measured or calculated b creatinine clearance (GFR can also be used in place of creatinine or CrCl)	$\leq 1.5 \times \text{ULN}$ OR $\geq 30 \text{ mL/min}$ for participant with creatinine levels $> 1.5 \times \text{institutional ULN}$
Hepatic	
Total bilirubin	$\leq 1.5 \times \text{ULN}$ OR direct bilirubin $\leq \text{ULN}$ for participants with total bilirubin levels $> 1.5 \times \text{ULN}$
AST (SGOT) and ALT (SGPT)	$\leq 2.5 \times \text{ULN}$ ( $\leq 5 \times \text{ULN}$ for participants with liver metastases)
Coagulation	
International normalized ratio (INR) OR prothrombin time (PT)	$\leq 1.5 \times \text{ULN}$ unless participant is receiving anticoagulant therapy as long as PT or aPTT is within therapeutic range of intended use of anticoagulants
Activated partial thromboplastin time (aPTT)	

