### 5.1.2 Participant Exclusion Criteria

Participants are excluded from the study if any of the following criteria apply:

1. A WOCBP who has a positive urine pregnancy test within 72 hours prior to treatment allocation (see Appendix 3). If the urine test is positive or cannot be confirmed as negative, a serum pregnancy test will be required.

*Note: in the event that 72 hours have elapsed between the screening pregnancy test and the first dose of study treatment, another pregnancy test (urine or serum) must be performed and must be negative in order for subject to start receiving study medication.*

2. Has received prior therapy with an anti-PD-1, anti-PD-L1, or anti-PD-L2 agent.
3. Has received chemotherapy, monoclonal antibody therapy, or targeted small molecule therapy within 4 weeks prior to the first dose of study medication. Subjects must have recovered ( $\leq$  Grade 1) from adverse events related to a previously administered agent (patients with  $\leq$  Grade 2 neuropathy are eligible). Subjects who have previously received CAR T cell therapy are eligible.

*Note: If a participant received major surgery, he or she must have recovered adequately from complications from the intervention prior to starting study treatment.*

4. Has received prior radiotherapy within 1 week of start of study treatment. Participants must have recovered from all radiation-related toxicities, not require corticosteroids, and not have had radiation pneumonitis.
5. Has a histologic diagnosis of primary mediastinal lymphoma or gray zone lymphoma.
6. Has known active CNS lymphoma and/or lymphomatous meningitis. Participants with previously treated brain metastases may participate provided they are radiologically stable, i.e. without evidence of progression for at least 4 weeks by repeat imaging (note that the repeat imaging should be performed during study screening), clinically stable and without requirement of steroid treatment for at least 14 days prior to first dose of study treatment.
7. Has received a live vaccine within 30 days prior to the first dose of study drug. Examples of live vaccines include, but are not limited to, the following: measles, mumps, rubella, varicella/zoster (chicken pox), yellow fever, rabies, Bacillus Calmette–Guérin (BCG), and typhoid vaccine. Seasonal influenza vaccines for injection are generally killed virus vaccines and are allowed; however, intranasal influenza vaccines (eg, FluMist®) are live attenuated vaccines and are not allowed.

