#### **Female Participants:**

Female participants of childbearing potential are eligible to participate if they agree to use a highly effective method of contraception consistently and correctly as described in Table 8 during the protocol-defined time frame in Section 6.0.

Table 8 Highly Effective Contraception Methods

Highly Effective Contraceptive Methods That Are User Dependent a  Failure rate of <1% per year when used consistently and correctly.

 
● Combined (estrogen- and progestogen- containing ) hormonal contraception b 
 
○ Oral
 
○ Intravaginal
 
○ Transdermal
 
○ Injectable
 
 
 
● Progestogen-only hormonal contraception b 
 
○ Oral
 
○ Injectable
 
 
 

Highly Effective Methods That Have Low User Dependency  Failure rate of <1% per year when used consistently and correctly.

 
● Progestogen- only contraceptive implant b
 
● Intrauterine hormone-releasing system (IUS)
 
● Intrauterine device (IUD)
 
● Bilateral tubal occlusion
 

 
● Vasectomized partner  A vasectomized partner is a highly effective contraception method provided that the partner is the sole male sexual partner of the WOCBP and the absence of sperm has been confirmed. If not, an additional highly effective method of contraception should be used.
 

 
● Sexual abstinence  Sexual abstinence is considered a highly effective method only if defined as refraining from heterosexual intercourse during the entire period of risk associated with the study treatment. The reliability of sexual abstinence needs to be evaluated in relation to the duration of the study and the preferred and usual lifestyle of the participant.)
 

Notes:  Use should be consistent with local regulations regarding the use of contraceptive methods for participants of clinical studies.
 
a) Typical use failure rates are lower than perfect-use failure rates (i.e. when used consistently and correctly).  b) If locally required, in accordance with Clinical Trial Facilitation Group (CTFG) guidelines, acceptable hormonal contraceptives are limited to those which inhibit ovulation.

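### Inclusion criterion 3 lists the negative pregnancy test as an alternative to the contraception agreement, which contradicts Appendix 4, where both are required

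*Combined protocol and SAP*

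**What the plan says.** Section 5.1.1 opens with the rule that joins the numbered criteria: "Participants are eligible to be included in the study if all of the following criteria apply". Within criterion 3 the joining rule changes. The woman must be neither pregnant nor "not breastfeeding, and at least one of the following conditions applies". Three items follow:

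- 3a: "Not a woman of childbearing potential (WOCBP) as defined in Appendix 4"
- 3b: "A WOCBP who agrees to follow the contraceptive guidance in Appendix 4 during the treatment period"; the commitment extends 120 days or more beyond the final dose
- 3c: "patient must have negative pregnancy test within 72 hours of beginning treatment if WOCBP"

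Section 5.1.2 covers nearby ground. Exclusion 1 removes "A WOCBP who has a positive urine pregnancy test within 72 hours prior to treatment allocation", asks for a serum test if the urine result is positive or unclear, and has a note requiring a fresh negative test if 72 hours pass before the first dose. Exclusion 22 removes women who are pregnant, breastfeeding or expecting to conceive.

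Appendix 4, under Contraception Requirements, says: "Female participants of childbearing potential are eligible to participate if they agree to use a highly effective method of contraception consistently and correctly". Under its Pregnancy Testing heading it separately allows a WOCBP into the study only after a negative urine or serum test.

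**The concern.** The words that introduce the list and the words of 3c pull in different directions. The introduction offers a choice. Item 3c says the patient must have the test. A site applying the introduction as written can accept the test in place of the contraception agreement. Criterion 2, for men, has no such choice: a male participant must agree to contraception.

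What is at stake is patient safety. Section 5.1.3.2 warns that pembrolizumab may harm a fetus in utero. A negative test before dosing shows only that the woman is not pregnant at that time; it says nothing about the months of treatment that follow. The rule on discontinuing treatment in pregnancy (Sections 5.1.4 and 5.6) acts only once a pregnancy has occurred.

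The wording may also be used twice. Entry to the Second Course (Section 5.2.3) refers back to the safety parameters in the inclusion criteria. The section does not say which criteria those are, so whether criterion 3 is among them is open.

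**Working it through.** No figure in the plan is involved, so there is nothing to recompute. The check is one of logic: apply criterion 3 as written, then look for other text that closes the gap.

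**Step 1. The rule as written.** For a woman who is neither pregnant nor breastfeeding, criterion 3 = (3a or 3b or 3c). For a WOCBP, 3a is false, so criterion 3 = (3b or 3c).

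**Step 2. The four possible cases for a WOCBP.**

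| Agrees to contraception (3b) | Negative test (3c) | Criterion 3 as written | Exclusions 1 and 22 | Appendix 4 |
|---|---|---|---|---|
| Yes | Yes | Met | Do not stop her | Satisfied |
| Yes | No | Met, through 3b | Stopped by exclusion 1 and its note | Not satisfied (test) |
| No | Yes | Met, through 3c | Do not stop her, unless she expects to conceive | Not satisfied (contraception) |
| No | No | Not met | Stopped by exclusion 1 and its note | Not satisfied (both) |

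The second row is harmless in practice, because exclusion 1 supplies the missing test. The third row is the defect.

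**Step 3. Does any exclusion close the third row?** Exclusion 1 concerns the test only. Exclusion 22 turns on expecting to conceive; a woman who does not expect to conceive but uses no contraception is outside it. Exclusion 20 lets the investigator exclude a patient whose participation is judged not in her best interest. That is a case-by-case judgement and does not mention contraception. No exclusion criterion requires the agreement.

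**Step 4. Compare with Appendix 4.** Appendix 4 makes the agreement a condition of eligibility for a WOCBP and states the test separately. Its rule is therefore (3b and 3c). Under that rule only the first row passes. Criterion 3 and Appendix 4 agree on the first and last rows and differ on the second and third. The exclusions remove the second difference but not the third.

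**The case against.** The best case for leaving the text alone is that the intended meaning can be recovered. Item 3c uses mandatory words and does not read naturally as a substitute for 3b. Criterion 3 points to Appendix 4 several times, and Appendix 4 states the contraception condition plainly. Exclusion 1 and the Pregnancy Testing text treat the test as an extra requirement. A careful investigator would probably ask for both. That is a fair account of the intent, and it limits the likely harm. It does not remove the contradiction: an eligibility rule should not depend on sites reading a choice as a joint requirement.

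Four stronger readings are tempting, and the documents do not support them.

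- *Such a woman is eligible for the trial.* She satisfies criterion 3 as worded, but under the protocol as a whole Appendix 4 would bar her.
- *The protocol drops its main safeguard.* The contraception requirement is still present in 3b and in Appendix 4. Only the logic of the list undermines it.
- *On-treatment pregnancy testing happens mainly after a missed period or on suspicion.* Appendix 4 also refers to time points in the Schedule of Activities and to local requirements. Part of the flow chart is illegible in the copy available, so the scheduled testing cannot be judged.
- *The size of the problem is the length of exposure.* Thirty-five doses every 3 weeks span 34 × 21 = 714 days from first to last dose, and adding 120 days gives 834. That is the longest period in which a fully treated patient could become pregnant while at risk. It does not measure the error or fetal exposure. The Trial Summary expects treatment to average 1 year, and Section 5.1.4 stops treatment at once on pregnancy.

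**Conclusion.** The point holds as an internal contradiction. Read literally, criterion 3 is met by a WOCBP with a negative test and no contraception agreement; no exclusion criterion closes that gap; and Appendix 4 says otherwise. It deserves correction because it lies in an operative eligibility rule that bears on patient safety.

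Its size cannot be calculated. The documents do not say how many women of childbearing potential are expected, or how sites will read the list. Planned enrolment is 13 to 29 participants, so the number affected is probably very small and may be zero. The endpoint, sample size, error rates and analysis are untouched.

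The conclusion rests on reading the introductory words of criterion 3 in their ordinary sense, and on the list in Section 5.1.1 being complete as shown; the introduction and all three items appear intact.

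**What to change.** Reconcile criterion 3 with Appendix 4 and exclusion 1. Keep 3a and 3b as the two alternatives. Take 3c out of that list and state it as its own requirement for every WOCBP. Then check that Section 5.1.1, exclusion 1 and Appendix 4 define the same eligible women, and that any eligibility checklist used at sites follows the revised text.

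Two clerical items can be settled in the same edit, though neither adds weight to this point. Exclusion 1 sends the reader to Appendix 3, which is the adverse-event grading appendix, while pregnancy testing is in Appendix 4. Table 8 note a, "Typical use failure rates are lower than perfect-use failure rates", appears to have its comparison reversed.

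The cost is a few lines of wording in the next amendment, with no change to the design or the analysis.
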